8.3 BLINDING PROCEDURES

8.3.1 Methods of blinding

This study has an open-label design. All enrolled patients will be on prior DMT when entering into the study and will be treated with alemtuzumab during alemtuzumab treatment phase. No randomization will be done.

The study will be rater-blinded for MRI. All brain scans will be reviewed and interpreted by one or more MRI experts at an independent, central facility with no access (ie, blinded) to treatment thereby avoiding bias. Refer to [Section 9.1.1.1](#) and [Section 9.2.1.1](#).

The MRI assessments will be available to the investigators to assess safety.

8.4 METHOD OF ASSIGNING PATIENTS TO TREATMENT GROUP

All enrolled patients will be on prior DMT when entering into the study and up to approximately 4 months. After this period all patients will stop their prior DMT and will be treated with alemtuzumab during alemtuzumab treatment phase.

No randomization will be performed.

An interactive voice response system (IVRS)/interactive web response system (IWRS) will be used for this study to manage and control alemtuzumab dispensation. The treatment kit number list is generated centrally by Sanofi. Alemtuzumab will be packaged in accordance with this list.

8.5 PACKAGING AND LABELING

Packaging will be in accordance with the administration schedule. The content of the labeling will be in accordance with the local regulatory specifications and requirements.

8.6 STORAGE CONDITIONS AND SHELF LIFE

Investigators or other authorized persons (eg, pharmacists) are responsible for storing alemtuzumab in a secure and safe place in accordance with local regulations, labeling specifications, policies and procedures.

Control of storage conditions for alemtuzumab will be provided by the Sponsor, especially control of temperature (eg, refrigerated storage) and information on in-use stability and instructions for handling alemtuzumab.

Alemtuzumab, in vials, must be stored between +2°C to + 8°C (+36°F to +46°F). Do not freeze and do not shake. Do not use alemtuzumab beyond the use by date provided on the label or other documentation. Protect from light.

Prior to administration, protect diluted alemtuzumab solution from light and store for as long as 8 hours either at room temperature 15°C to 25°C (59°F to 77°F) or keep refrigerated at conditions 2°C to 8°C (36°F to 46°F). From a microbiological point of view, it is recommended that the product should be used immediately. Partially used, unused or damaged drug vials should be disposed according to institutional policies.

Alemtuzumab will be used in accordance with the approved protocol and must not be used for any other purpose.

8.7 RESPONSIBILITIES

The Investigator, the hospital pharmacist, or other personnel allowed to store and dispense the IMP will be responsible for ensuring that the IMP used in the clinical trial is securely maintained as specified by the Sponsor and in accordance with applicable regulatory requirements.

All IMP will be dispensed in accordance with the Investigator's prescription and it is the Investigator's responsibility to ensure that an accurate record of IMP issued and returned is maintained.

Any quality issue noticed with the receipt or use of an IMP (deficiency in condition, appearance, pertaining documentation, labeling, expiration date, etc) must be promptly notified to the Sponsor (see [Section 10.4.7](#)). Some deficiencies may be recorded through a complaint procedure.

A potential defect in the quality of IMP may be subject to initiation of a recall procedure by the Sponsor. In this case, the Investigator will be responsible for promptly addressing any request made by the Sponsor, in order to recall the IMP and eliminate potential hazards.

Under no circumstances will the Investigator supply IMP to a third party, allow the IMP to be used other than as directed by this clinical trial protocol, or dispose of IMP in any other manner.

8.7.1 Treatment accountability and compliance

As alemtuzumab will be administered by daily IV infusions in a day hospital supervised medical setting, by qualified center personnel, responsibility for compliance with mandatory safety assessments resides with the Study Investigator.

8.7.2 Return and/or destruction of treatments

For IMP provided by the Sponsor:

Reconciliation of all used, partially-used or unused treatments must be performed at the site by the Investigator and the monitoring team using treatment log forms.

Written authorization for destruction will be given by the sponsor once the reconciliation has been completed. This destruction can be performed at the site depending on local regulations and site specific capabilities; alternatively, study drug may be returned to the sponsor or designee for destruction. The Investigator will not destroy the used and unused IMP unless the Sponsor provides written authorization.

8.8 CONCOMITANT MEDICATION

A concomitant medication is any treatment received by the patient concomitantly to any IMP(s). Concomitant treatments have been detailed for all phases of the study and are not limited to the treatment received with the IMP (treatment phase). Concomitant use of alternative medications (eg, herbal treatments, botanicals, etc) for treatment of MS is discouraged due to concerns of possible interactions with study treatment. Patients should be questioned about their use of such nonprescription therapies, all of which will be listed as concomitant medications.

Prior DMT period

Therapy with disease-modifying MS treatments that the patient is currently being administered (ie, limited to interferons and GA only) will be permitted during the screening and prior DMT Treatment Phase. If the investigator determines that the patient needs to be treated with another DMT, the patient will be discontinued from the study.

Prior DMT will be discontinued 7 days before alemtuzumab first administration. Refer to [Section 6.1](#) for further details.

No concomitant therapy with any other disease-modifying MS treatments either licensed or investigational will be permitted during the screening and prior DMT period.

Concomitant use of systemic corticosteroids for the treatment of MS relapse is allowed during the DMT period.

Alemtuzumab treatment phase

Patients who receive any alemtuzumab treatment will continue study participation even if they do not complete the planned treatment regimen. Patients who discontinue study treatment can continue study participation. If a patient is not willing to continue study participation, all efforts should be made to have the EOTP visit performed by the patient.

No concomitant therapy with any disease-modifying MS treatments either licensed or investigational, including interferons and GA, will be permitted during the alemtuzumab treatment phase. If the investigator determines that the patient needs to be treated with another DMT, the patient will be discontinued from the study.

In addition, no other investigational MS therapy, including investigational symptomatic therapy, will be permitted. Use of live vaccines is specifically prohibited for alemtuzumab-treated patients for the 30 days prior to the first alemtuzumab administration at Month 0 and for the 2 years duration of the alemtuzumab treatment phase of the study.

Concomitant use of systemic corticosteroids for the treatment of MS relapse is allowed during this period.

Safety monitoring phase

The safety of MS disease-modifying drugs in patients who receive alemtuzumab has not been established. Alemtuzumab treatment may have long-lasting, unknown effects on a patient's immune system. Concomitant therapy with any disease-modifying MS treatments following treatment with alemtuzumab has not been studied in a controlled study conducted by Sanofi Genzyme. Investigators should consider the potential for adverse effects associated with subsequent or concomitant treatment with cytotoxic or immunosuppressant drugs in patients who have received alemtuzumab.

Participating patients are prohibited from use of any investigational MS therapy.

It is investigator criteria to determine if the patient needs to be treated with another DMT, and in which case the patient will be discontinued from the study.

Concomitant use of systemic corticosteroids for the treatment of MS relapse is allowed during the course of the Study. Relapses may be treated with systemic corticosteroids if clinically necessary and as per Investigator judgment in doses appropriate for paediatric population.

The use of systemic corticosteroids or adrenocorticotrophic hormone within 2 weeks prior to MRI assessment is not permitted due to potential interference with MRI assessment.

It is recommended that patients complete local immunization requirements at least 6 weeks prior to treatment with alemtuzumab. The ability to generate an immune response to any vaccine following alemtuzumab treatment has not been studied.

The safety of immunization with live viral vaccines following a course of alemtuzumab treatment has not been formally studied in controlled clinical trials in MS. Live vaccines must not be administered to MS patients who have recently received a course of alemtuzumab. Also, some experts urge caution in using live pathogen vaccinations in people with MS (National MS Society web site).

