STUDY DESIGN	
Open-label, rater-blinded, single-arm, before and after switch study of efficacy, safety and tolerability of alemtuzumab in paediatric patients from 10 to <18 years of age with RRMS with disease activity on prior DMT.
 
The study will consist of:
 
 Screening period (0-28 days prior to M-4) - This phase consists of the screening assessments for study eligibility of patients on current DMT. Prior DMT phase (approximately 4 months) - This phase consists of the efficacy measurements on current DMT, which will be used as comparator group in the study. Subjects will continue the use of their current DMT (limited to beta interferon therapy [IFNB] or glatiramer acetate [GA]) during this period until 7 days prior to administration of first dose of alemtuzumab at M0. Alemtuzumab treatment phase (approximately 2 years) - This phase starts with administration of first dose of alemtuzumab at M0, after discontinuation of current DMT, and ends at M24. The second dose of alemtuzumab will be administered at M12. The MRI based primary efficacy endpoint will be assessed over a 4 month period during the treatment phase compared to an equal period during the prior DMT phase. Note: EOTP refers to the end of the Alemtuzumab Treatment Phase. Safety monitoring phase (approximately 3 years) - Additional safety follow-up and monitoring for all patients treated with alemtuzumab will be conducted during this phase to yield a total of 5 years of follow-up since first alemtuzumab

	
treatment, including 4 years post last treatment with alemtuzumab.
 
 Note: EOS refers to the end of the safety monitoring phase.

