6 STUDY DESIGN

6.1 DESCRIPTION OF THE STUDY

This is an open-label, rater-blinded, single-arm, before and after switch study of efficacy, safety and tolerability of alemtuzumab in paediatric patients from 10 to <18 years of age with RRMS with disease activity on prior DMT.

The study will consist of:

- **Screening period** (0-28 days prior to M-4) - Patients and parents will receive information on the study and on alemtuzumab. Inclusion/exclusion criteria will be reviewed. After informed consent signature, screening assessments for eligibility will be performed. Screening assessments may require more than one visit within the screening period which may last a maximum of 28 days.
- **Prior DMT phase (approximately 4 months): M-4 to M0**
 - **Eligibility confirmation visit:** At the end of the screening period (at M-4) patients/parents will come to the site to confirm patient is eligible for the study. Investigator will check that all assessment allow patient inclusion. During this visit patients will be reminded to continue their prior DMT (limited to interferon or GA only).
 - **From M-4 visit to D-14 to D-7:** Phone calls (approximately every month) will be done, to remind patients to continue on their DMT and check patient status.
 - **Day -14 to D-7 visit:** Investigator will confirm patient is eligible for alemtuzumab administration and will tell the patient to discontinue current DMT 7 days prior to administration of first dose of alemtuzumab at Month 0.
- **Alemtuzumab treatment phase** (approximately 2 years) – This phase starts with administration of first dose of alemtuzumab at M0, after discontinuation of current DMT, and ends at M24. The second dose of alemtuzumab will be administered at M12. The MRI based primary efficacy endpoint will be assessed over a 4 month period during this phase compared to an equal period during the prior DMT phase.

Note: end of treatment phase (EOTP) refers to the end of the alemtuzumab treatment phase (see graphic study design [[Section 1.1](#)]).
- **Safety monitoring phase** (approximately 3 years) – Additional safety follow-up and monitoring for all patients treated with alemtuzumab will be conducted during this phase to yield a total of 5 years of follow-up since first alemtuzumab treatment, including 4 years post last treatment with alemtuzumab.

Note: end of study (EOS) refers to the end of the safety monitoring phase (see graphic study design [[Section 1.1](#)]).

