6.2 DURATION OF STUDY PARTICIPATION

6.2.1 Duration of study participation for each patient

The maximum study duration per patient will be approximately 5 years and 5 months:

- **Screening period:** 0-28 days prior to M-4 from signed informed consent to eligibility confirmation.
- **Prior DMT phase:** approximately 4 months from signed informed consent and screening qualification to prior DMT discontinuation. **Alemtuzumab treatment phase:** approximately 2 years, from first dose alemtuzumab administration to one year after last dose of alemtuzumab administration.
- **Safety monitoring phase:** approximately 3 years to complete the 48 months safety follow-up post last treatment with alemtuzumab.

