10.1.18 Visit 28/M24 EOTP

The following assessments should be done as listed in the study flow chart:

- AE/SAE will be monitored (if any).
- Concomitant medication will be checked and reported (if any).
- Physical examination including vital signs.
- Blood samples collection for clinical laboratory assessments including thyroid function test, ADA, and urinalysis.
- Blood samples collection for lymphocyte phenotyping.
- Blood samples collection for immune markers (optional).
- Perform Tanner staging.
- Perform MRI scan without contrast.
- Perform EDSS assessment.
- Perform SDMT and BVMT-R test.
- Recording of PedsQL/Ped NeuroQoL.

10.1.19 Safety monitoring phase Year 3 to Year 5

The following assessments should be done as listed in the study flow chart:

- AE/SAE will be monitored (if any).
- Perform EDSS assessment at every 6 months.

- Concomitant medication will be checked and reported (if any).
- Physical examination including vital signs at every 6 months.
- Blood sample collection for hematology, urinalysis, ALT, and serum creatinine every month.
- Perform clinical chemistry assessments including thyroid function test every 3 months.
- Perform MRI scan without contrast, PedsQL/Ped NeuroQoL, and cognitive tests yearly.
- Perform Tanner staging yearly.
- Blood samples collection for lymphocyte phenotyping and ADA yearly.

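### Section 8.8 removes from the study any alemtuzumab-treated patient who needs another DMT, in conflict with the planned 5-year safety follow-up of all treated patients

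*Protocol*

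**What the plan says.** **The follow-up plan.** The clinical trial summary (Study design) states: "Additional safety follow-up and monitoring for all patients treated with alemtuzumab will be conducted during this phase". Section 6.1 gives the length: "to yield a total of 5 years of follow-up since first alemtuzumab treatment, including 4 years post last treatment with alemtuzumab". Section 6.2.1 describes the roughly 3-year safety monitoring phase as there "to complete the 48 months safety follow-up post last treatment with alemtuzumab". None of these places makes an exception for patients who change therapy.

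**The tests.** Section 4 says that thyroid tests every 3 months, and monthly blood counts, creatinine and urinalysis, must continue until 48 months after the last infusion. Section 10.1.19 schedules this for Years 3 to 5: "Blood sample collection for hematology, urinalysis, ALT, and serum creatinine every month" and "Perform clinical chemistry assessments including thyroid function test every 3 months".

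**The exit rule.** Section 8.8, treatment phase, begins "No concomitant therapy with any disease-modifying MS treatments either licensed or investigational, including interferons and GA" and continues "will be permitted during the alemtuzumab treatment phase. If the investigator determines that the patient needs to be treated with another DMT", with discontinuation from the study as the consequence. Its safety monitoring paragraph repeats this: the investigator judges whether another DMT is needed, "and in which case the patient will be discontinued from the study". Neither paragraph provides for safety follow-up afterwards.

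**The concern.** The protocol plans complete safety follow-up for everyone who receives alemtuzumab, and separately orders the removal of one group of those patients. This is not ordinary dropout, because the protocol itself ends the observation. It is also selective: the patients removed are those judged to need further treatment, in a cohort enrolled for disease activity on an earlier DMT.

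Safety is part of the primary objective (Section 5.1), and the safety endpoint runs for up to 4 years after the last dose. The monitoring exists to detect delayed autoimmune events. Section 8.8 itself says that the safety of other DMTs after alemtuzumab is not established, which is a reason to go on observing these children. An analysis plan cannot recover visits that never took place.

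**Working it through.** **1. Reproduce the planned horizon.** Course 2 is at M12 and follow-up runs 48 months after it: 12 + 48 = M60. The safety phase starts at M24 and lasts about 36 months: 24 + 36 = M60, and 60/12 = 5 years. Adding about 1 month of screening and 4 months on prior DMT gives 1 + 4 + 60 = 65 months, the stated 5 years 5 months. The plan's own figures agree with each other.

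**2. Loss per switcher after both courses.** For a switch at month x, months forgone = 60 − x, with one monthly panel per month. Quarterly thyroid tests forgone = (60 − x)/3, counting a test due at x as done.

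| Switch at | Months and monthly panels forgone | Thyroid tests forgone | Share of the 48 months after Course 2 |
|---|---|---|---|
| M18 | 60 − 18 = 42 | 42/3 = 14 | 42/48 = 87.5% |
| M24 | 60 − 24 = 36 | 36/3 = 12 | 36/48 = 75% |
| M36 | 60 − 36 = 24 | 24/3 = 8 | 24/48 = 50% |

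**3. Switch after Course 1 only (last dose at M0).** Against the 5-year plan, M6 forgoes 60 − 6 = 54 months and M10 forgoes 60 − 10 = 50. Against 48 months from last dose, the figures are 48 − 6 = 42 and 48 − 10 = 38.

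**4. Year 3.** A switch at or before M24 misses all 12 monthly panels after M24 up to M36, and all 4 thyroid tests (M27, M30, M33, M36).

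**5. Scale.** Assume 50 treated patients, the planned evaluable number: 50 × 60 = 3000 patient-months. One switch at M18, M24 or M36 removes 42/3000 = 1.4%, 36/3000 = 1.2% or 24/3000 = 0.8%. The protocol gives no switch rate, so this cannot be turned into a cohort figure without an assumption. If 5% to 30% of the 50 switched, at times from M36 back to M12, the loss would run from 2.5 × 24 = 60 patient-months (2%) to 15 × 48 = 720 (24%). That range only shows how far the answer depends on the assumed rate.

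**6. Does another section restore the follow-up?**
- Sections 10.3 and 10.3.4, and the retention sentence in 8.8, mainly concern patients who stop or do not complete alemtuzumab, not patients ordered out of the study.
- Section 10.4.3 follows existing adverse events to resolution or stabilisation. It does not test for new ones.
- Section 10.3.5 asks for one end-of-study assessment, if possible.
- Section 10.4.4 covers serious events after study end only if they reach the investigator and are judged to be caused by the drug.
- Section 11.3.2 counts patients who do not complete the safety phase, with reasons.

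None of these replaces the scheduled monitoring.

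**The case against.** **The 5 years is a plan, not a guarantee.** The durations are approximate, Section 6.2.1 gives a maximum, the endpoint says up to 4 years, and Section 11.3.2 expects non-completers. This stands as far as voluntary withdrawal goes. It does not explain a mandatory removal that the follow-up statements never mention.

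**The rule keeps attribution clean.** Section 8.8 places it next to a statement that DMTs after alemtuzumab are unstudied, and Section 11.4.3.1 counts every event from first dose to M60 as on treatment. The difficulty is real, but separate reporting before and after DMT start deals with it without discarding observation.

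**Stronger readings that the documents do not support.**
- A reader might infer that all safety information stops at the switch. It does not: the provisions of Sections 10.3.5, 10.4.3 and 10.4.4 remain.
- A reader might infer that these children go clinically untested. Section 4 states the 48-month testing requirement without tying it to study participation. What is lost is the study's scheduling and systematic collection.
- A reader might infer that most thyroid events would be missed. Section 4 does put the highest adult incidence in Year 3, but the same sentence reports no consistent pattern of onset, and the paragraph puts serious thyroid events below 1% of patients.
- A reader might infer a large loss for the cohort. No switch rate is given.
- A reader might infer damage to the primary MRI comparison. Switches after M8 do not touch it.

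**Conclusion.** The conflict is real and stands in current text. Section 8.8 ends study participation for treated patients whom the summary, Section 6.1 and Section 6.2.1 plan to follow, and for whom Section 4 requires tests to 48 months after the last infusion. Per patient the loss is substantial: half or more of the 48 months after Course 2 for any switch up to M36. The cohort-level size is unknown. The per-patient percentages of total follow-up assume 50 treated patients.

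This should be fixed, because the loss is selective, falls on primary-objective safety data and is cheap to avoid. The matching sentence for the prior DMT period is not at issue, since those patients have not yet received alemtuzumab.

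**What to change.** In the treatment-phase and safety-monitoring-phase paragraphs of Section 8.8, replace the withdrawal clause. A patient who needs another DMT stops alemtuzumab permanently, receives no further course, and continues scheduled safety follow-up to M60, subject to consent.

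Keep the general treatment-phase ban on concomitant DMTs and the bans on investigational MS therapy. Allow one exception: a licensed DMT that the investigator judges necessary, which triggers the permanent stop. It would be wrong to limit the ban to the time when further alemtuzumab is planned. Course 2 at M12 is the last planned course, so the ban would lapse for every patient from then on, and freely added DMTs could contaminate the Year 2 relapse rate and EDSS.

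Record the DMT and its start date. In Section 11.4.3.1, report adverse events overall and separately before and after DMT start. Leave the handling of relapse and EDSS data after the switch to the SAP, and leave the prior-DMT-period sentence unchanged.

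**Cost.** A protocol amendment with ethics and authority approval and possible re-consent. The visits are already in the schedule, so the running cost is the planned visits of patients who switch. Events after a switch will be harder to attribute, which the split reporting addresses.
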